12. PHARMACOKINETIC EVALUATION

The pharmacokinetic (PK) concentration data will be summarized on the PK population for the protocol scheduled sampling time points:

- Baseline: 0-hour (pre-dose), 1-hour post-dose and 6-hour post-dose
- Week 4: 0-hour (pre-dose), 2-hour post-dose and 4-hour post-dose

Descriptive statistics of PK concentration (mean, standard deviation, coefficient of variation (CV) % mean, geometric mean, CV (%) geometric mean, median, minimum and maximum values) will be calculated at each time point. A listing for PK concentration data will also be provided.

The PK parameters will be derived and estimated based on measured teduglutide plasma concentrations using a population PK modeling approach by a Takeda designated vendor in accordance with the PK SAP.

T:\Shire\Teduglutide\XXA39799\Biostatistics\Documentation\SAP\SHP633-302 SAP Final Document:

1.0 17Apr2019.docx

Template No: CS TP BS016 Revision 4

Effective Date: 01Apr2016

Version Date: 17Apr2019

Version Number:

Reference: CS WI BS005

Final 1.0

Author:

13. SAFETY EVALUATION

All safety evaluations will be conducted on the Safety population. By-visit summaries will include all protocol scheduled visits during the 24-week treatment period, EOT and Week 28 visit.

13.1. EXTENT OF EXPOSURE

The extent of exposure is defined as the number of days on treatment, calculated as: (date of last dose - date of first dose) + 1.

The first dose date and last dose date will be based on the eCRF. The extent of exposure, the number of days that the dose was administered will be summarized. The number and percentages of subject will be tabulated for extent of exposure categorized into weeks (<4, 4-<12, 12-<24 and ≥24). Exposure summaries will be presented for the ITT and Safety populations.

The information related to the study drug training provided by the study physician will be listed for all subjects in the Safety population.

13.2. ADVERSE EVENTS

Adverse Events (AEs) will be coded using MedDRA. Investigator verbatim as well as preferred term and system organ class will be included in the listings.

Treatment emergent AEs (TEAEs) are defined as AEs whose onset occurs, severity worsens or intensity increases during or after receiving the study medication. AEs with an unknown date of onset and a stop date after the start of the study period or unknown will be included as treatment emergent AEs. Any AE with a start date equal to the date of first dose, where the time of the AE cannot definitively place the start of the AE prior to the first dose, will be considered treatment emergent. If any AE records contain only partial dates, these will be handled by imputation, as described in Section 6.3. AEs which are not treatment emergent will be flagged in listings.

AEs will be summarized overall using descriptive statistics (e.g., number and percent of subjects). The number of events will also be presented. Categories summarized will include any TEAE (Y/N), severity of TEAEs (any and highest category), investigator assessment of relationship of TEAEs to study treatment, treatment emergent serious AEs (TESAEs), severity of TESAEs, investigator assessment of relationship of TESAEs to study treatment, TEAEs leading to death, TEAEs leading to discontinuation, and TEAEs of special interest.

Treatment emergent AEs will be summarized using number and percentage of subjects. Subject incidence for AEs within each SOC and PT will be presented, unless otherwise

Document: T:\Shire\Teduglutide\XXA39799\Biostatistics\Documentation\SAP\SHP633-302 SAP Final

1.0 17Apr2019.docx

Template No: CS_TP_BS016 Revision 4

Effective Date: 01Apr2016

Author:

Version Number: Version Date: Final 1.0 17Apr2019

Reference: CS_WI_BS005

specified. The number of events will also be summarized. Categories summarized will be the same as those summarized in the overview tabulations, except that no summary table will be provided for TEAEs leading to death. Presentation by SOC and PT will present SOC sorted alphabetically and PT within SOC by descending incidence.

Summaries of TEAEs, TEAEs by relationship, TESAEs and TESAEs by relationship will also be presented by PT. These presentations will be sorted by descending incidence.

For the summaries described above, TEAEs with a missing severity will be classified as severe and TEAEs with a missing relationship to study drug will be regarded as related to study drug.

In addition, AEs of special interest will be considered. An AE of special interest is an AE (serious or nonserious) of scientific and medical concern specific to the sponsor's product or program. The AEs of special interest will include the following groupings:

- Growth of pre-existing polyps of the colon
- Benign neoplasia of the GI tract including the hepatobiliary system
- Tumor-promoting ability (e.g., benign and/or malignant neoplasia of any kind, not limited to those of the GI or hepatobiliary system)

The MedDRA terms corresponding to each grouping of events of special interest are included in APPENDIX 3.

The number and percentage of subjects with at least one TEAE of special interest will be presented. The number of events of special interest will also be summarized.

Listings will be provided for serious adverse events (SAEs), AEs leading to death, AEs leading to discontinuation of study drug and AEs of special interest.

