2.1. STUDY DESIGN

This will be an open-label, 24-week study, in which subjects will receive 0.05 mg/kg/day of teduglutide. The study population will include 2 cohorts: infants 4-<12 months corrected gestational age and children 1-15 years of age.

All subjects will be screened for a minimum of 2 weeks prior to start of treatment to verify the requirements for nutritional support for each subject and to ensure adherence to eligibility parameters. Attempts should be made to limit the screening period to 4 weeks.

After screening, the 24-week treatment period will consist of visits at baseline, weekly for the first 2 weeks, and then every other week through week 12. For the remainder of the treatment period, visits at the sites will be conducted every 3 weeks. Scheduled telephone contacts will be made on all other weeks during the treatment period. At all site visits and during telephone contacts, safety will be monitored and nutritional support will be reviewed and adjusted as needed. The end of study (EOS) visit will be scheduled at week 28, 4 weeks following end of treatment (EOT). Weekly telephone contact will be made during the interim weeks from EOT to EOS to monitor safety and any changes in nutritional support.

To maintain consistency across all centers, all attempts should be made to follow the nutritional support adjustment guidelines and weaning algorithms (developed with SBS expert input and provided in the protocol) for decisions regarding parenteral nutrition/intravenous fluids (PN/IV) support reduction and advances in enteral feeds based on weight gain, urine, and stool output in the setting of clinical stability. Any departure from the nutritional support adjustment guidelines and weaning algorithms will not constitute a protocol deviation.

A schematic representation of the study design is displayed in Figure 1. The study schedule of events can be found in Table 1 and Table 2 of the protocol.

Figure 1 Study Diagram

[figure not shown]
Document: T:\Shire\Teduglutide\XXA39799\Biostatistics\Documentation\SAP\SHP633-302 SAP Final

1.0_17Apr2019.docx

Author: Version Number: Final 1.0 Version Date: 17Apr2019

Template No: CS_TP_BS016 Revision 4 Reference: CS_WI_BS005

Effective Date: 01Apr2016

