6.3. HANDLING OF DROPOUTS OR MISSING DATA

All subjects in the analysis population defined in Section 7 will be included in the associated analyses.

No imputation for missing data (e.g., last observation carried forward [LOCF]) will be applied except for the partial dates for adverse events and prior/concomitant medications.

Details on how to handle partial dates for adverse events and prior/concomitant medications are described below.

Complete dates will be imputed from partial dates of adverse events and medications solely for the purpose of defining treatment emergence for adverse events and prior/concomitant status for medications (Imputed dates will not be presented in the listings). Dates will be defined using the hierarchy of derivations below.

Adverse event or medication start date (references to month and year are the month and year of the start date):

- 1. If year and month are known, and it is the month and year of the first dose date, use the first dose date.
- 2. If year and month are known, and it is not the month and year of the first dose date, use the first day of the month.
- 3. If only year is known, and it is the year of the first dose date, use the first dose date.
- 4. If only year is known, and it is not the year of the first dose date, use the first day of the year (1st January).
- 5. Should any of the previous start dates created be after a complete stop date provided, use the stop date as the start date, instead of the date that would otherwise be created.
- 6. For medication start date, if "Before Informed Consent" is ticked then use the date of informed consent.
- 7. Otherwise, if start date is unknown leave as missing.

Adverse event or Medication stop date (references to month and year are the month and year of the stop date):

Document: T:\Shire\Teduglutide\XXA39799\Biostatistics\Documentation\SAP\SHP633-302 SAP Final

1.0 17Apr2019.docx

Version Number: Version Date: Final 1.0 17Apr2019

Reference: CS WI BS005

Author:

Template No: CS TP BS016 Revision 4

Effective Date: 01Apr2016

- 1. If year and month are known, use the last day of the month.
- 2. If only year is known, use the last day of the year (31st December).
- 3. Otherwise, if stop date is unknown leave as missing.

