6.4. INTERIM ANALYSES AND DATA MONITORING

An interim analysis of subjects 1-15 years of age will be performed at the completion of their participation.

Safety and tolerability results will be evaluated by a Data Monitoring Committee (DMC) which will convene approximately every 3 months during the active study period (date of the first subject's first dose to date of the last subject's last dose), based on subject enrollment. The DMC review will include all cumulative safety data from study assessment through the end of each review period.

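### Two date rules in the SAP can count adverse events that ended before the first dose as treatment emergent: an undefined 'study period' test in 13.2 and a stop-date check in 6.3 limited to complete dates

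*SAP*

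**What the plan says.** SAP section 13.2 defines treatment-emergent events as "AEs whose onset occurs, severity worsens or intensity increases during or after receiving the study medication". It then adds a treatment-emergence rule for missing onset dates: "AEs with an unknown date of onset and a stop date after the start of the study period or unknown will be included". An event starting on the day of first dose is also treatment emergent unless its recorded time places it before the dose.

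Section 6.3 completes partial dates for this classification. For a start date, rule 3 reads: "If only year is known, and it is the year of the first dose date, use the first dose date". Rule 5 is the safeguard: "Should any of the previous start dates created be after a complete stop date provided, use the stop date as the start date". For a partial stop date the rule is: "If year and month are known, use the last day of the month". Nothing in the list checks the start date again once a partial stop date has been completed.

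On timing, section 2.1 states: "All subjects will be screened for a minimum of 2 weeks prior to start of treatment". Sites are asked to try to keep screening to 4 weeks. The nearest defined term to study period is in section 6.4, on the data monitoring committee: "active study period (date of the first subject's first dose to date of the last subject's last dose".

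**The concern.** An event that stopped before the first dose, with no later worsening, cannot meet the definition in 13.2. Two rules nevertheless let such an event through.

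The first tests the stop date against the start of an undefined period instead of the subject's first dose. The second moves a vague start date to the day of first dose and overlooks a stop month that shows the event was already over.

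A misclassified event would enter the TEAE summaries by system organ class, preferred term, severity and relationship, and the serious-event summaries where it applies. If its severity or relationship is also missing, 13.2 counts it as severe or as related. The cohorts are very small, so a single record is visible in a percentage.

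**Working it through.** The plan gives no figure to reproduce. The check applies its rules to illustrative records.

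**Assumed subject.** Screening from 10 April 2018 and first dose on 5 May 2018, which is 25 days. This lies between the 2-week minimum and the 4-week target in section 2.1. The first subject in the trial is assumed to have been dosed on 10 January 2018.

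**Rule in 13.2: unknown onset, complete stop date 28 April 2018 (7 days before first dose).**

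| Study period starts at | Stop date after it? | Result |
|---|---|---|
| Subject's screening, 10 April 2018 | Yes | TEAE |
| First subject's first dose, 10 January 2018 (term in 6.4) | Yes | TEAE |
| Subject's own first dose, 5 May 2018 | No | Not TEAE |

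Only the third reading agrees with the definition in 13.2. If the period starts at screening, the stop dates wrongly accepted are those after the first screening day and before the first dose. With S days of screening there are S − 1 of them: 14 − 1 = 13 and 28 − 1 = 27. Four weeks is a target, so 27 is not a strict upper limit.

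**Rules in 6.3: partial dates, same subject.**

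| Recorded start | Recorded stop | Start used | Stop used | Result as written | Result if rule 5 also uses the imputed stop |
|---|---|---|---|---|---|
| 2018 | 28 Apr 2018 | 28 Apr (rule 3, then rule 5) | 28 Apr | Not TEAE | Not TEAE |
| 2018 | Apr 2018 | 5 May (rule 3; rule 5 not triggered) | 30 Apr | **TEAE, starting after it ended** | Start becomes 30 Apr: not TEAE |
| May 2018 | May 2018 | 5 May (rule 1) | 31 May | TEAE | TEAE |

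The first row shows that rule 5 works as intended when the stop date is complete. The second row is the gap. The third row is truly ambiguous and is rightly kept as a TEAE either way.

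The gap is confined to one pattern: a year-only start in the first-dose year with a month-and-year stop before the first-dose month. A year-only stop is completed to 31 December, so it cannot precede a first dose in the same year. If the start month is the first-dose month, a consistent stop month cannot be earlier.

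**Effect on a percentage.** The PK analysis plan, section 5, gives planned minimums of 5 children and 2 infants. One affected subject with no other event of the same preferred term adds 1/5 = 20 percentage points in children or 1/2 = 50 in infants.

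**The case against.** The strongest reply is that study period in 13.2 may simply mean the subject's time on drug. The sentences around it refer to study medication and to the first dose date, and on that reading the rule is harmless. This stands to the extent that the first fault depends on an undefined term. It does not settle the matter: the SAP calls on-drug time the treatment period, uses first dose date freely in 6.3, and defines the nearest term from the first subject's first dose.

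A second reply is that the records are rare. The SAP does not say when adverse event collection begins. If it begins at consent, an event that ended months before dosing would be medical history. A reader might infer that the whole calendar year before dosing is exposed under 6.3, but the document does not support that. On the consent assumption the window is a screening period that crosses a month boundary, as in the example, and the site would have to know the stop month but only the start year. That is possible but unusual.

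A reader might also infer that the same gap turns prior medications into concomitant ones. It does not. Start rule 6 covers medications ticked as begun before consent, and section 13.10 defines prior medications by when they were discontinued. At most, a record without that tick meets both definitions.

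Nor do the adverse event tables compare time before dosing with time after it. They present treatment-emergent events, and the others are flagged in listings. The error is also conservative, and the recorded partial dates stay visible because imputed dates are not listed. All of this limits the harm, but none of it makes the rules agree with the definition.

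**Conclusion.** The point holds in a limited form. Under 13.2, an event of unknown onset that resolved in screening is counted as a TEAE unless study period means the subject's own first dose, which the SAP does not say. It would go too far to state that the rule certainly misclassifies such events. Under 6.3 the fault needs no interpretation: the one pattern shown above yields a TEAE whose imputed start falls after its stop.

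The frequency cannot be given, because it depends on the number of incomplete dates and on when event collection starts. It should be low, and the direction is over-counting of harm. The possible shift of 20 or 50 percentage points rests on the planned minimum cohort sizes and on the subject having no other event of that term. Counting an affected event as severe or related needs a further missing field on the same record. The change should be made because the rules can contradict the definition they serve and correcting them is nearly free.

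**What to change.** In section 13.2, replace the test against the start of the study period with a stop date on or after the date of the subject's first dose. In section 6.3, let start rule 5 use the complete or imputed stop date: where that date falls before the imputed start, it becomes the start.

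Keep as treatment emergent any event whose stop date is unknown, or whose complete or imputed stop date is on or after the first dose. This preserves the conservative handling of ambiguous timing. Because rule 5 also serves medications, the same edit removes the overlap between prior and concomitant.

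The cost is two wording changes and about one line of derivation code. No new data are needed.

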13.3. Clinical Laboratory Evaluation

Laboratory evaluations that are done at study site visits will be collected and processed via a central laboratory, and presented in standard international (SI) units. Laboratory evaluations that are required at intervals that do not coincide with study site visits may be obtained by a local laboratory. The local laboratory data will be collected on the local laboratory tests form of eCRF.

Clinical laboratory evaluations include, but not limited to, the following:

Document: T:\Shire\Teduglutide\XXA39799\Biostatistics\Documentation\SAP\SHP633-302 SAP Final

1.0 17Apr2019.docx

Template No: CS TP BS016 Revision 4

Effective Date: 01Apr2016

Author:

P_BS016 Revision 4 Reference: CS_WI_BS005 2016

Version Number:

Version Date:

Final 1.0

17Apr2019

Copyright © IQVIA. All rights reserved.

IMS Health & Quintiles are now

Chemistry:

- o Albumin
- Alkaline phosphatase
- Alanine aminotransferase
- Amylase
- Aspartate aminotransferase
- o Bicarbonate
- Bilirubin (total, direct and indirect)
- o Blood urea nitrogen
- o Calcium (total)
- Chloride
- o Cholesterol
- C-reactive protein
- Creatinine
- Estimated glomerular filtration rate (Schwartz formula)
- o Gamma-glutamyl transferase
- Glucose
- Lipase
- o Magnesium
- o Phosphorus
- o Potassium
- o Sodium
- Triglycerides
- Uric acid

· Hematology:

- Hematocrit
- Hemoglobin
- Platelet count
- o Red blood cell (RBC) count
- RBC morphology, if needed
- White blood cell count with differential
- Coagulation:
 - Prothrombin time/International normalized ratio
- Urinalysis:

Author:

- Blood
- Glucose
- Leucocytes
- Microscopic analysis

Document: T:\Shire\Teduglutide\XXA39799\Biostatistics\Documentation\SAP\SHP633-302 SAP Final

1.0 17Apr2019.docx

Template No: CS_TP_BS016 Revision 4

Effective Date: 01Apr2016

Version Number: Version Date: Final 1.0 17Apr2019

Reference: CS_WI_BS005

- pH and osmolality
- o Protein
- Specific gravity

The laboratory summaries will be based on central lab results only and be presented for scheduled site visits only, i.e., baseline, weeks 1, 2, 4, 6, 8, 10, 12, 15, 18, 21, 24 and 28. In addition, laboratory results will also be presented at EOT.

Quantitative results will be summarized for hematology, serum chemistry, and selected urinalysis parameters by scheduled site visit. Both observed values and change from baseline will be summarized with descriptive statistics defined in Section 6.1. Quantitative laboratory measurements reported as "< X", i.e. below the lower limit of quantification (BLQ), or "> X", i.e. above the upper limit of quantification (ULQ), will be converted to X for the purpose of quantitative summaries, but will be presented as recorded, i.e. as "< X" or "> X" in the listings.

Markedly abnormal laboratory values are defined in APPENDIX 1. These criteria are based on lab normal ranges. The number and percentage of subjects with post-baseline results qualifying as markedly abnormal as defined in this table will be summarized by parameter and a subject level listing will be presented.

Laboratory results will be presented in an appendix data listing for each lab panel (chemistry, hematology, urinalysis) by subject, parameter, and date of collection. Laboratory values outside of the normal range will be flagged. Local lab test results, categorical test results and urine pregnancy results will be presented in appendix data listings only.

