6. STATISTICAL/ANALYTICAL ISSUES

6.1. GENERAL METHODOLOGY

All statistical procedures will be completed using SAS version 9.4 or later.

Document: T:\Shire\Teduglutide\XXA39799\Biostatistics\Documentation\SAP\SHP633-302 SAP Final

1.0 17Apr2019.docx

Author: Version Number: Final 1.0 Version Date: 17Apr2019

Template No: CS_TP_BS016 Revision 4 Reference: CS_WI_BS005

Effective Date: 01Apr2016

Copyright © IQVIA. All rights reserved.

Due to the limited size of the study population descriptive statistics will be used with a goal of summarizing the sample which discourages the use of inferential statistics. Accordingly, no claims of significance will be made for any of the data.

Continuous variables, including those assessed on a discrete scale, will be summarized using descriptive statistics including number of subjects, mean, median, standard deviation, maximum, and minimum. Standard errors (SE) will be displayed for the efficacy tables, and body weight, height (or length), BMI, head circumference and weight for length. For categorical variables, descriptive statistical summaries will include number of subjects and percentages.

For summary purposes, the baseline value will be defined as the last available pre-dose value. Scheduled visits will be summarized as provided in the electronic case report forms (eCRFs). An End of Treatment (EOT) time point, defined as the last determination of endpoint or last available measurement after the date of first dose during the 24-week treatment period will be analyzed in addition to the scheduled visits. Similarly, an End of Study (EOS) time point will be defined as the last determination of endpoint or last available measurement after the EOT during the 4-week follow-up period. Unscheduled measurements will not be included in by-visit summaries, but can contribute to the EOT/EOS value where applicable.

Study Day will be calculated as follows:

- If the date of the evaluation is on or after the first day of study medication then: Study Day = (date of the evaluation – first day of study medication) + 1.
- If the date of the evaluation is prior to the first day of study medication then: Study Day = (date of the evaluation – first day of study medication).

Datasets and listings will include data collected at unscheduled visits. Data collected at unscheduled visits will not be included in summaries by timepoint or visit unless specified otherwise.

Data will be analyzed and presented by subject cohorts:

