APPENDIX 1. MARKEDLY ABNORMAL LABORATORY CRITERIA

Lab Parameter	Unit	`	- <12 months estational age)	Children (1 - 15 years)		
		Lower Limit Criteria	Upper Limit Criteria	Lower Limit Criteria	Upper Limit Criteria	
Chemistry						
Albumin	g/L	<20	>68	<20	>68	
Alkaline Phosphatase	U/L		>5 x ULN		>5 x ULN	
Alanine Aminotransferas e (ALT)	U/L		>8 x ULN		>8 x ULN	
Aspartate Aminotransferas e (AST)	U/L		>8 x ULN		>8 x ULN	
Amylase	U/L		>3 x ULN		>3 x ULN	
Lipase	U/L		>3 x ULN		>3 x ULN	
Bilirubin Total	umol/L		>5 x ULN		>3 x ULN	
Direct Bilirubin	umol/L		>68.4147		>34.208	
Blood Urea Nitrogen	mmol/L		>12.495		>12.495	
Calcium	mmol/L	<1.5	>3	<1.5	>3	
Creatinine	umol/L)	>132.6		>132.6 if age < 10 y; >150.28 if age 10- <13 y; >176.8 if age 13-<16 y; >221 if age 16+	
C Reactive Protein	mg/L		>=100		>=100	
Glucose	mmol/L	<2.22	>13.875	<2.22	>13.875	
Magnesium	mmol/L	<0.4114	>1.2342	<0.4114	>1.2342	
Phosphorus	mmol/L	<0.644	>2.254	<0.644	>2.254	

Document: T:\Shire\Teduglutide\XXA39799\Biostatistics\Documentation\SAP\SHP633-302_SAP_Final

1.0_17Apr2019.docx Author:

Template No: CS TP BS016 Revision 4

Effective Date: 01Apr2016

Version Date: 17Apr2019

Reference: CS_WI_BS005

Final 1.0

Version Number:

Copyright © IQVIA. All rights reserved.

Potassium	mmol/L	<2.5	>6.5	<2.5	>6.5
Sodium	mmol/L	<120	>160	<120	>160
Triglycerides	mmol/L		>5.65		>5.65
Hematology					
Hemoglobin	g/L	<70	>200	<70	>200
Hematocrit	fraction of 1	<0.21	>0.60	<0.21	>0.60
Platelets	10^9/L	<75	>700	<75	>700
Leukocytes	10^9/L	<2	>30	<2	>30
Neutrophils, absolute	10^9/L	<0.5		<0.5	

1.0_17Apr2019.docx

Template No: CS_TP_BS016 Revision 4

Effective Date: 01Apr2016

Author:

Copyright © IQVIA. All rights reserved.

The contents of this document are confidential and proprietary to IQVIA. Unauthorized use, disclosure or reproduction is strictly prohibited.

Document: T:\Shire\Teduglutide\XXA39799\Biostatistics\Documentation\SAP\SHP633-302 SAP Final

Version Number: Version Date:

Final 1.0 17Apr2019

Reference: CS_WI_BS005

APPENDIX 2. L, M and S Values of Height, Body Weight, BMI and Head Circumference for Age for Japanese

Table 1 L, M and S Values of Height for Age for Japanese Children

Age (yr) -		Male			Female	
Age (y1)	L	\mathbf{M}	S	L	\mathbf{M}	S
0	2.300	49.0	0.0417	1.200	48.5	0.0390
0.25	2.212	61.5	0.0378	1.159	60.1	0.0361
0.5	2.124	67.7	0.0351	1.117	66.2	0.0341
0.75	2.036	71.6	0.0335	1.076	70.2	0.0327
1	1.948	74.8	0.0328	1.034	73.5	0.0318
1.25	1.861	77.8	0.0328	0.993	76.6	0.0316

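### The markedly abnormal laboratory table ignores baseline status, so it cannot separate a persisting pre-treatment abnormality from a new one

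*SAP*

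**What the plan says.** SAP Section 13.3 gives the counting rule: "The number and percentage of subjects with post-baseline results qualifying as markedly abnormal as defined in this table will be summarized by parameter". The limits are in Appendix 1, which lists 23 parameters (18 chemistry, 5 hematology) with fixed cut-offs or multiples of the upper limit of normal. Direct bilirubin is an example, with the infant limit first and the children's limit second: "Direct Bilirubin umol/L >68.4147 >34.208". No entry carries a condition on the baseline value.

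Other displays in Section 13.3 do bear on baseline:

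- For quantitative results by visit, "Both observed values and change from baseline will be summarized with descriptive statistics defined in Section 6.1".
- For the markedly abnormal results, "a subject level listing will be presented".
- More generally, "Laboratory results will be presented in an appendix data listing for each lab panel", ordered by subject, parameter and collection date, with values outside the normal range flagged.

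Section 6.1 defines baseline: "the baseline value will be defined as the last available pre-dose value". For adverse events, Section 13.2 uses a different logic and counts as treatment-emergent those whose "onset occurs, severity worsens or intensity increases during or after receiving the study medication".

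**The concern.** A child beyond an Appendix 1 limit before the first dose, who remains beyond it on treatment, is counted exactly like a child who crosses the limit for the first time on treatment. That holds even if the first child is improving. Nothing in the planned table shows which of the two a count represents.

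In a controlled trial the comparison arm would show the background rate. Section 2.1 describes an open-label study in which every subject receives teduglutide, so the within-subject baseline has to do that work. The subjects have short bowel syndrome and depend on parenteral support, so abnormal chemistry or hematology before treatment is plausible. With cohorts this small, a single such subject can set the printed percentage.

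The SAP takes baseline into account in its other categorical safety displays: adverse events by onset or worsening (13.2), ECG findings tabulated at baseline and later visits (13.5), and antibody status tabulated at baseline and later visits (13.7). The markedly abnormal laboratory count has neither a new-or-worse rule nor a baseline row.

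**Working it through.** The SAP states no figure to reproduce. The sample size rests on feasibility (Section 3) and the analysis is descriptive (Section 6.1). The check is therefore a reading of the counting rule, followed by arithmetic for scale.

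**Inputs**

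- Counting rule: any post-baseline result meeting an Appendix 1 limit (Section 13.3).
- Default denominator: all subjects in the analysis set (Section 15.2).
- Planned minimum enrolment: 5 children and 2 infants (PK Analysis Plan, Section 5).
- Default table columns: children after Amendment 3, total children, infants (Section 15.2).
- Baseline prevalence of markedly abnormal values: not given. The values below are assumptions.

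**Step 1. What the rule counts**

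| Baseline | Post-baseline | Counted in 13.3? | New since baseline? |
|---|---|---|---|
| Within limit | Beyond limit | Yes | Yes |
| Beyond limit | Still beyond, unchanged or improving | Yes | No |
| Beyond limit | Still beyond, worse | Yes | No, but worsened |
| Beyond limit | Back within limit at every post-baseline sample | No | No |

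The first three rows give the same entry in the table. The fourth shows that a pre-treatment abnormality is carried over only if it persists or recurs.

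**Step 2. Weight of one carried-over case**

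- Children: 1/5 = 20.0%, with 0 new events among the 4 subjects who could have one.
- Infants: 1/2 = 50.0%, with 0 new events among the 1 subject who could have one.

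The documents do not give the size of the children's subset after Amendment 3, on which Section 6.1 bases the main conclusions. If it is below 5, one case weighs more there.

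**Step 3. Chance of at least one such subject at baseline**

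For one given criterion with assumed baseline prevalence p and n independent subjects, the chance is 1 − (1 − p)^n. For example, with n = 5 and p = 0.10 it is 1 − 0.90^5 = 41.0%.

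| Assumed p | 5 children | 2 infants |
|---|---|---|
| 2% | 9.6% | 4.0% |
| 5% | 22.6% | 9.8% |
| 10% | 41.0% | 19.0% |
| 20% | 67.2% | 36.0% |

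These are chances of meeting the criterion before treatment. The chance of being carried into the count is at most this, because the abnormality must also be present after baseline.

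**The case against.** The strongest reply has four parts.

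1. **The table does what it says.** It reports post-baseline values beyond a limit. It is not labelled treatment-emergent or drug-related, and Section 6.1 disclaims any claim of significance. The adverse event definition does not govern laboratory tables. This stands: the SAP makes no false statement here, and the point concerns what the table can show.

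2. **Baseline information is available elsewhere.** The by-visit summaries include baseline and report minimum and maximum (Sections 6.1 and 13.3), and with 2 infants those two statistics give both values. The dated listings let a reader check each flagged subject. This largely stands. A reader might infer that this count is the only summary of extreme values, or that the safety question cannot be answered. The documents support neither. What remains is that in the larger cohort a visit's minimum and maximum do not show whether the flagged subject was already beyond the limit, and Section 13.3 does not say that the subject-level listing shows baseline status. The shells are in a separate file (Section 16), so the listing layout cannot be judged.

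3. **The frequency is unknown.** Many limits are extreme, such as more than 8 times the upper limit of normal for ALT and AST, and eligibility limits in the protocol may exclude some subjects. This stands, and it is why Step 3 is only a range under assumptions. A reader might also pool the cohorts and quote 2/7 = 28.6%, but Section 15.2 lists no pooled column by default.

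4. **Counting only new crossings would lose information.** A subject slightly beyond a limit at baseline who deteriorates on treatment is counted now and would drop out of a count restricted to new crossings. This stands and rules out replacing the existing count.

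**Conclusion.** The point holds as a minor reporting weakness. The markedly abnormal count takes no account of baseline, so the table alone cannot separate persisting from new abnormality in a study without a control group. One carried-over case amounts to 20.0 percentage points in a cohort of 5 children or 50.0 points in a cohort of 2 infants. Those sizes are enrolment minimums; larger cohorts would reduce the effect. Whether any such case occurs depends on a baseline prevalence that the documents do not give.

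A reader might infer that carried-over cases dilute a true signal. They do not remove any new case: they add to the numerator, and every case is still listed by subject. The loss is in interpretation of the printed number and percentage. No efficacy result is affected.

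**What to change.** In Section 13.3, keep the existing count of subjects with any post-baseline value beyond the limit, on its existing denominator. For each parameter and direction (low, high), add:

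- (a) the number of subjects meeting the criterion at baseline;
- (b) the number newly meeting it post-baseline, among subjects with a baseline value that did not meet it and at least one post-baseline value.

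State that subjects with a missing baseline do not enter row (b). In the subject-level listing, show the baseline value and a flag for baseline status, so that worsening in a subject already beyond the limit stays visible.

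The data are already collected. Of the 23 parameters in Appendix 1, 11 have both a lower and an upper limit and 12 have one, giving 2 × 11 + 12 = 34 parameter-direction pairs and up to 2 × 34 = 68 added rows. Row (b) needs a parameter-specific denominator, which must be footnoted because it departs from the default in Section 15.2. Otherwise the change is a few sentences in the SAP and an update to the shells.
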